6 ANALYSIS OF SAFETY

All safety parameters will be summarized based on the FAS Population.

6.1 Adverse Events

Adverse events data is collected from the time that informed consent was given, for the duration of the trial on the 'Adverse Events' eCRF page. All events in the clinical database regardless of when they occurred will be provided in data listings. Adverse events will be classified according to the MedDRA to the levels of SOC and PT. SOC will be sorted alphabetically and PT within each SOC will be sorted by overall descending order of frequency.

Pre-treatment AEs are defined as AEs that started during the pre-treatment period (date of informed consent up to the time before the first administration of the study product. Pre-treatment AEs, if any, will be listed only.

Treatment-emergent adverse events (TEAEs) are those with onset after the first dose of study product. Only treatment-emergent events will be summarized.

An overall summary will be presented which gives the number and percentage of subjects that experienced any TEAE, experienced any treatment related TEAE, permanently discontinued treatment due to a TEAE, interrupted treatment due to a TEAE, experienced a serious AE (SAE), and AEs leading to death.

The number and percentage of subjects experiencing one or more events will be tabulated by SOC and PT. In addition, similar tables by SOC and PT will be displayed further by maximum severity, and by closest relationship to treatment. For summary, the TEAEs with relationship to treatment reported as "None" or "Unlikely" are considered "Not Related", and "Possible", "Probable", or "Highly Probable" are considered "Related".

Summary tables will be prepared also for the number and percentage of subjects experiencing one or more events classified as: On Treatment Period (AEs started between the day of first administration of the study product and the day of last administration of the study product), and On Follow-up Period (AEs started after the day of last administration of the study product).

In summary tables for ocular adverse events, AEs occurring in both eyes will be summarized once at the greater severity or closer relationship to study drug.

The number of and percentage of subjects experiencing AEs leading to premature discontinuation from the study will be tabulated and listed.

Confidential Final Version 1.0, 2021-05-20

A listing of serious TEAEs will be also provided.

A glossary listing that shows the verbatim terms assigned to each SOC and PT will be provided.

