8.3. RECORDING

AEs will be collected and recorded for any untoward event that occurs in a patient from the time he or she signs the ICF for the trial until 24 weeks after the last dose of Study Product. Thus, any untoward medical occurrences or unfavorable and unintended signs, symptoms, or diseases that occur in the pretreatment, treatment, or post treatment period are to be considered AEs and/or SAEs, and consequently recorded and reported as such. Should a non-serious AE become serious, the Investigator will then follow the same reporting procedures as for SAEs.

Each AE will be described by:

- Its duration (start and stop dates)
- Severity
- Its relationship to the study drug; (suspected/unsuspected)
- Action(s) taken
- Outcome

Medical conditions/diseases, or cancer related signs/symptoms present before starting study treatment shall be documented in the medical history section of the CRF; these conditions are considered AEs only if they increase either in frequency or severity once informed consent has been signed.

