8.3.3. Severity of AEs

The Investigator will grade the severity of any AE using the definitions in the **Table** below. For each episode, the highest severity grade attained should be reported.

Severity of the Adverse Event

Mild	Grade 1 - Does not interfere with patient's usual function (awareness of symptoms or signs, but easily tolerated [acceptable]).	
Moderate	Grade 2 - Interferes to some extent with patient's usual function (enough discomfort to interfere with usual activity [disturbing]).	
Severe	Grade 3 - Interferes significantly with patient's usual function (incapacity to work or to do usual activities [unacceptable])	

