1.3.4 Safety Assessments

1.3.4.1 Adverse events

Adverse events (AEs) will be collected and recorded for any untoward event that occurs in a patient from the time he or she signs the ICF for the trial until 24 weeks after the last dose of Study Product. Thus, any untoward medical occurrences or unfavorable and unintended signs, symptoms, or diseases that occur in the pretreatment, treatment, or post treatment period are to be considered AEs and/or SAEs, and consequently recorded and reported as such. Should a non-serious AE become serious, the Investigator will then follow the same reporting procedures as for SAEs. Each AE will be recorded for duration

Confidential

Final Version 1.0, 2021-05-20

(start and stop dates), severity, relationship to the study drug, action(s) taken, outcome.

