2.3 Study Period, Visit, and Day

The overall study consists of initial Screening, a 14-day Washout Period, an 8week Treatment Period, and a 24-week Follow-up Period.

A reference date refers to the date of the first study product administration. All safety and efficacy assessments at all visits will be assigned a day relative to this date. The relative day will be defined as: visit date – reference date + 1 for visits on or after the reference date, and visit date – reference date for visits before the reference date.

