| 14.2.6.2 | Percentage of Patients Achieved a 15- letter Gain in BCDVA at 4, 8 and 32 weeks | Full Analysis Set |
| 14.2.7 | IDEEL Change from Baseline to Weeks 4, 8, and 32 | Full Analysis Set |
| 14.2.8 | EQ-5D-5L Change from Baseline to Weeks 4, 8, and 32 | Full Analysis Set |

Confidential

Statistical Analysis Plan

Protocol: NGF0120

| 14.2.9 | Exposure of Artificial Tears during the Follow-up Period | Full Treated Set |
|----------|--|-------------------|
| 14.3.1.1 | Summary of Treatment-Emergent Adverse Events | Full Analysis Set |
| 14.3.1.2 | Frequency of Treatment-Emergent Adverse Events by System Organ Class and Preferred Term | Full Analysis Set |
| 14.3.1.3 | Frequency of Treatment-Emergent Adverse Events by System Organ Class and Preferred Term and by Maximum Severity | Full Analysis Set |
| 14.3.1.4 | Frequency of Treatment-Emergent Adverse Events by System Organ Class and Preferred Term and by Closest Relatedness | Full Analysis Set |
| 14.3.1.5 | Frequency of Treatment-Emergent Adverse Events Leading to Permanent Withdrawal of Study Medication by System Organ Class and Preferred Term | Full Analysis Set |
| 14.3.1.6 | Adverse Event - MedDRA Glossary | Full Analysis Set |
| 14.3.2 | Listing of Serious Treatment Emergent Adverse Events | Full Analysis Set |
| 14.3.3 | Intraocular Pressure Change from Baseline to Weeks 8 and 32 | Full Analysis Set |
| 14.3.4 | Frequency Summary of Slit-Lamp Examination Results | Full Analysis Set |
| 14.3.5 | Frequency Summary of External Ocular Examination Results | Full Analysis Set |

List of listings

| Listing | Listing Title | Analysis |
|------------|---|-------------------|
| Number | | Population |
| 16.2.1.1 | Subject Disposition | Screened |
| 16.2.1.2 | Screen Failures | Screened |
| 16.2.1.3 | Analysis Visits | Full Analysis Set |
| 16.2.2.1 | Inclusion and Exclusion Criteria Exceptions | Full Analysis Set |
| 16.2.2.2 | Protocol Deviations | Full Analysis Set |
| 16.2.3 | Analysis Populations | Full Analysis Set |
| 16.2.4.1 | Demographics | Full Analysis Set |
| 16.2.4.2.1 | Medical History | Full Analysis Set |
| 16.2.4.2.2 | Ocular History | Full Analysis Set |
| 16.2.4.2.3 | Initial Diagnosis Neurotrophic Keratitis or Keratopathy | Full Analysis Set |
| 16.2.4.3.1 | Prior Medications | Full Analysis Set |
| 16.2.4.3.2 | Concomitant Medications | Full Analysis Set |
| 16.2.5.1 | Treatment Exposure of Study Product | Full Analysis Set |

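### SAP 6.1 defines TEAEs by onset date with no worsening clause, so an adverse event that starts in washout and worsens on drug can be missing from the TEAE tables and the serious-TEAE listing

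*SAP*

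**What the plan says.** **Collection.** SAP 1.3.4.1 and Protocol 8.3 collect AEs "from the time he or she signs the ICF for the trial until 24 weeks after the last dose of Study Product". SAP 2.3 places "a 14-day Washout Period" before treatment, so AEs can be opened before any study product is used.

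**Classification.** SAP 6.1 sorts AEs by start date. Those that start between consent and first administration are pre-treatment, and "Pre-treatment AEs, if any, will be listed only". For the rest, "Treatment-emergent adverse events (TEAEs) are those with onset after the first dose of study product". The section adds that "Only treatment-emergent events will be summarized". Protocol 7.1.3 names TEAEs as a safety endpoint but does not define them.

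**Recording.** Protocol 8.3.3 says "For each episode, the highest severity grade attained should be reported". Protocol 8.3 says "Should a non-serious AE become serious, the Investigator will then follow the same reporting procedures as for SAEs". Neither section says whether a worsening opens a new record or takes a new onset date.

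**Outputs.** In SAP Appendix 2, Tables 14.3.1.1 to 14.3.1.5 are titled as treatment-emergent. Item 14.3.2 is "Listing of Serious Treatment Emergent Adverse Events". Listing 16.2.7 holds all AEs.

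**The concern.** A TEAE definition usually has two limbs: new onset after dosing, and worsening after dosing of something already present. SAP 6.1 has only the first. With AE collection open during washout, the second limb matters: patients stop their topical eye medication at Visit 1, so ocular complaints may begin before the first dose. The product's listed common effects (eye pain, redness, inflammation, tearing) are of a similar kind.

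Safety is part of the primary objective, and the study has one arm, so no comparator is undercounted in the same way. If a worsening on drug is filed under a pre-dose start date, it is missing from the tables by preferred term, maximum severity and relatedness. If it became serious, it is also missing from the serious-event listing.

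**Working it through.** The plan gives no figure to reproduce. The check is to follow one hypothetical patient through the rules. An ocular AE starts as mild during washout and becomes severe, or serious, during treatment.

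| Step | Kept as one record | Worsening entered as a new record |
|---|---|---|
| Start date | In washout | After first dose |
| Severity (Protocol 8.3.3) | Severe, the highest grade of the episode | Severe, on the new record |
| Class under SAP 6.1 | Pre-treatment | TEAE |
| Tables 14.3.1.1 to 14.3.1.4 | Not counted | Counted |
| Table 14.3.1.5, if study product is stopped for it | Not counted | Counted |
| Item 14.3.2, if serious | Not listed | Listed |
| Listing 16.2.7 | Listed | Listed |

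The same clinical course gives 0 or 1 in the tables, depending only on data entry. Four checks on whether other text closes the gap:

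1. **Protocol 8.3** treats conditions present before treatment as AEs only if they increase in frequency or severity after consent. That decides when a condition becomes an AE. It gives no new start date to an AE already open.
2. **Protocol 8.1** includes exacerbation of preexisting conditions or events in the AE definition. This allows a new record but does not require one.
3. **SAP 2.11** moves a completely missing start date to first administration unless the stop date shows that the event ended earlier. The gap therefore concerns events with a known washout start. The contrast is awkward: an ongoing AE with no start date counts as treatment-emergent, while one known to have started just before dosing and then turned severe does not.
4. **Protocol 9.3.3** plans AE, SAE and discontinuation summaries without a TEAE limit. SAP section 1 says that the SAP supersedes the protocol's statistical text, and SAP section 9 declares no changes, so the narrower rule governs without being flagged as a change.

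**Size of one omitted patient.** Safety uses the FAS, meaning all dosed patients (SAP 2.6.3 and 6). The 35 in the plan counts patients who complete 8 weeks, and Protocol 6.2 replaces those who stop earlier. If the target is met, the FAS is therefore at least 35:

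100 × 1/N ≤ 100 × 1/35 = 2.9 percentage points per omitted patient.

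The documents give no rate of washout-onset AEs that worsen on drug, so the number of such patients is unknown. SAP 5.4 plans confidence intervals for efficacy only, so no planned safety interval is affected.

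**The case against.** The best counter-argument rests on Protocol 8.1 and 8.2. An exacerbation of a preexisting event is itself an AE, and a clinically relevant untoward change in a protocol parameter must be reported as one. If sites apply this by opening a new record, its onset is post-dose and the present definition captures it. Protocol 8.3.3 does not define an episode, and the eCRF completion instructions are not among the documents. This stands to the extent that the loss is conditional: a reader might infer that a worsening always keeps its pre-dose start date, and the text does not say so. It equally does not say the opposite, and that is the weakness.

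A reader might also infer that such events vanish from every safety output. They do not. Listing 16.2.7 includes them, and the IOP, slit-lamp and external-examination summaries do not use the TEAE definition. In SAP 6.1, the SAE and death rows of the overall summary and the tabulation of study discontinuations are worded as AEs, not TEAEs. Against the blanket limit to TEAEs, those items are ambiguous and not clearly excluded.

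A third tempting reading is that the word after in the definition conflicts with an On Treatment Period that begins on the day of first administration. This is minor wording: an event later on that day satisfies both, and SAP 2.11 already treats a start date imputed to that day as treatment-emergent.

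Finally, the study is descriptive and tests no hypothesis, so no formal inference is affected. That limits the consequence but does not make the counts right.

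**Conclusion.** The concern holds in conditional form. SAP 6.1 has no worsening clause, and neither document fixes how a worsening of an open AE is recorded. Where a site keeps one record, a washout-onset AE that worsens or becomes serious on drug is left out of Tables 14.3.1.1 to 14.3.1.5 and item 14.3.2, while remaining in listing 16.2.7. Compared with a definition that includes worsening, the present rule can only lower the counts, and it leaves them dependent on site habit. Each affected patient is worth at most 2.9 percentage points, assuming that at least 35 patients are dosed. The number affected cannot be estimated from the documents. This should be corrected because safety is in the primary objective and the correction is cheap, not because a large effect has been shown.

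**What to change.** 1. **SAP 6.1.** Define a TEAE as an AE with onset on or after the first dose, or an AE with earlier onset that increases in severity, frequency or seriousness on or after the first dose. Apply this to Tables 14.3.1.1 to 14.3.1.5 and item 14.3.2.
2. **eCRF completion guide.** Instruct sites to record the worsening with its date. Without this the new definition cannot be programmed: a single record with only its highest grade does not show whether the peak came before or after dosing. A mandatory new line would catch most cases even under the present definition, but the definition should state the intent.
3. **SAP 6.1, overall summary.** State one consistent rule, AE or TEAE, for the SAE, death and study-discontinuation items, and reconcile it with the sentence limiting summaries to TEAEs.

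The cost is one definition sentence and a consistency statement in the SAP, one line in the eCRF guide, and possibly slightly higher TEAE counts. Design, sample size and efficacy analyses are unchanged.

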6.2 Intraocular Pressure

Descriptive statistics of the observed and change from baseline IOP (mmHg) will be summarized as a continuous variable for study eye and treated non-study eye by visit.

6.3 Slit Lamp Examination

Categorical results of slit lamp examination will be summarized for each parameter in a frequency table for study eye and treated non-study eye by visit. Following parameters will be included: Anterior Chamber Cells, Anterior Chamber Flare, Anterior Chamber Other Abnormal Finding, Conjunctiva Edema, Conjunctiva Bulbar Erythema, Conjunctiva Other Abnormal Finding, Cornea Edema, Cornea Endothelial Changes, Cornea Epithelial Changes, Cornea Other Abnormal Finding, Iris, Iris Other Abnormal Finding, Lashes, Lens, Lens Other Abnormal Finding, Eyelid Edema, Eyelid Erythema, Eyelid Other Abnormal Finding, Sclera, Sclera Other Abnormal Finding.

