Rescue Therapy: Commercially available preservative free artificial tears (AT) provided by Sponsor are not allowed during the treatment period. Per the investigator's discretion if the patient requires rescue therapy during the 8-week treatment period then they can receive artificial tears provided by the sponsor for up to four times per day. The frequency of rescue therapy must be documented in the patient's diary.

The study will be a total of 34 weeks in duration: a screening period of 2 weeks, followed by 8 weeks of treatment and a 24-week follow-up period. At the end of the screening period (at Visit 2), patients meeting the entry criteria for this study will be assigned to treatment with OXERVATE[™] 0.002% (20

mcg/mL) cenegermin-bkbj ophthalmic solution which will be known as Study Product beginning the morning following Visit 2.

Following the completion of the treatment period, patients will be followed up for an additional 24 weeks (for patients healed and non-healed [and not meeting d/c criteria] at Week 8) and will be evaluated at the end of the follow-up period. At the investigator's discretion, the subject may be seen for an Unscheduled Visit to evaluate for safety. Patients who prematurely discontinue for whatever reason will not be followed post discontinuation and should have Visit 6 assessments completed.

At Visit 1, eligible patients will be instructed to discontinue all topical ophthalmic medications and will only be allowed to use commercially available preservative free tears provided by the sponsor to be used up to four times per day during the screening period. At the conclusion of the Baseline Visit (Visit 2) eligible patients will be dispensed a 2-week supply of Study Product from the onsite freezer in a sealed bag and will be instructed to self-administer the Study Product one drop six times a day starting on the day after Day 0/ Visit 2 through Week 8 of the controlled treatment period according to the dosing schedule shown in Table 1 (Dosing Schedule).

Table 1 Dosing Schedule

TREATMENT	TREATMENT DOSING SCHEDULE*
OXERVATE™ 0.002% (20 mcg/mL) cenegermin-bkbj ophthalmic solution	Morning (8 AM)
	Mid-morning (10 AM)
	Noon (12 PM)
	Early afternoon (2 PM)
	Mid afternoon (4 PM)
	Late afternoon (6 PM)

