Patients who meet the definition of Deterioration or No Improvement in the study eye at week 8 and during the follow up period, will be discontinued from the study and treated as appropriate at the discretion of the investigator.

Deterioration or No Improvement is defined by any of the following:

- In the Study Eye, the FCS is unchanged (Grade=3) from baseline in the qualifying NEI zone.
- At the PIs discretion, in the study eye there is a progression from baseline in the non-qualifying zones
- decrease in BCDVA by >10 ETDRS letters from baseline.
- progression in staining to a PED or corneal melting or perforation
- onset of infection
- Require an ocular surgical procedure, including the need for a corneal transplant.

Note: If there is a deterioration in the non-study eye, the Investigator may discontinue treatment in that eye and initiate alternative treatment at their discretion in the non-study eye, but continue following the study eye per protocol.

[figure not shown]
All patients will attend the following clinic visits in the following sequence:

- Screening (Visit 1/Day -14)
- Baseline and First Study Product Pick-Up (Visit 2/Day 0)
- Product Pick-Up (Visit 3/Week 2)
- Treatment Assessment and Study Product Pick-Up (Visit 4/Week 4)
- Product Pick-Up (Visit 5/Week 6)
- End of 8-week Treatment (Visit 6/Week 8)
- Follow-Up and Final Study Visit (Visit 7/Week 32).

The trial structure for subjects is shown in **Figure 1**

Figure 1 Study Schematic

Any subject who meets the definition of experiencing a deterioration in the study eye, will be discontinued from the study, and followed per the Investigator's discretion.

If there is a deterioration in the non-study eye, the Investigator may discontinue treatment in that eye and initiate alternative treatment at their discretion in the non-study eye, but continue following the study eye per protocol.

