2.9 Descriptive Summaries

Summary statistics and statistical analyses will generally be performed only for subjects included in the relevant analysis population. For the calculation of summary statistics and statistical analysis, unrounded data will be used. For endpoints that are continuous in nature: number of observations, mean, median, minimum and maximum, and standard deviation (SD) values will be presented as descriptive statistics summary for both observed values and change from baseline values at each scheduled visit if applicable. For endpoints that are categorical in nature: frequency counts and percentages will be presented as descriptive statistics summary at each scheduled visit if applicable.

The number of decimal places to display for calculated data will be determined by the original scale of the data. Means and medians will be reported with one (1) additional decimal place. Standard deviation will be reported with two (2) additional decimal places. Minimum and maximum will be reported with the same number of significant digits as the method of capture.

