6.4 External Ocular Examination

Categorical results of external ocular examination will be summarized for each parameter in a frequency table for study eye and treated non-study eye by visit. Following parameters will be included: Motility of extraocular muscles, Appearance of eyelids, Specific mechanism.

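### Slit lamp and external eye findings are tabulated only as by-visit frequencies; a paired shift from baseline would be a minor, cheap improvement

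*SAP*

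**What the plan says.** SAP 6.3 states that categorical slit lamp results "will be summarized for each parameter in a frequency table for study eye and treated non-study eye by visit". SAP 6.4 does the same for the other examination: "Categorical results of external ocular examination will be summarized for each parameter in a frequency table", again by visit for study eyes and treated non-study eyes. Both follow the default for categorical data in SAP 2.9, under which "frequency counts and percentages will be presented as descriptive statistics summary at each scheduled visit if applicable".

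SAP Appendix 2 lists one table for each examination, both on the Full Analysis Set: Table 14.3.4, "Frequency Summary of Slit-Lamp Examination Results", and Table 14.3.5, "Frequency Summary of External Ocular Examination Results". The list contains no shift table and no count of newly abnormal or worsened eyes. For intraocular pressure, SAP 6.2 does plan a comparison with baseline: "Descriptive statistics of the observed and change from baseline IOP (mmHg) will be summarized as a continuous variable".

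Two rules in Protocol 3.3 decide which eyes reach Week 32. The first concerns deterioration or a lack of improvement: anyone meeting that definition "in the study eye at week 8 and during the follow up period, will be discontinued from the study". The second is that "Patients who prematurely discontinue for whatever reason will not be followed post discontinuation".

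**The concern.** Safety is part of the primary objective (Protocol 3.1) and the trial has a single arm. Without a control group, each eye's own baseline is the natural reference for a new finding. By-visit frequencies discard that pairing. If some eyes clear while others become abnormal, the percentage can stay flat or even fall.

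What is at stake is limited: the tabulated visibility of low-grade findings. Bulbar erythema, conjunctival edema and eyelid edema are among the parameters in SAP 6.3, and the package insert (Protocol Appendix 3) names ocular hyperemia and swelling among the common side effects. A shift from normal to abnormal but not clinically significant is the kind of change that need not become an adverse event. As planned, it could be traced only in the listings.

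**Working it through.** The plan gives no figure on this point. Its one design figure, the lower confidence limits in Protocol 9.1, reproduces (Clopper-Pearson, n = 35: 40.2% at 58% and 54.3% at 72%, against the stated 40% and 54%), but nothing below depends on it.

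**Inputs.** The number of eyes is set at n = 35 for illustration. That is the planned number of 8-week completers (Protocol 9.1), not the size of the Full Analysis Set, which includes everyone dosed. It may be larger, because patients who stop before completing 8 weeks are replaced (Protocol 6.2). The documents give no abnormality rates, so all counts of abnormal eyes are assumed.

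**Step 1: what the margins identify.** Let b eyes be abnormal at baseline and v at a later visit, among the same n eyes. The number newly abnormal lies between max(0, v − b) and min(v, n − b), out of n − b eyes at risk.

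| b | v | Table shows | Newly abnormal | Of at-risk eyes |
|---|---|---|---|---|
| 3 | 3 | 8.6% and 8.6% | 0 to 3 of 32 | 0% to 9.4% |
| 5 | 5 | 14.3% and 14.3% | 0 to 5 of 30 | 0% to 16.7% |
| 5 | 3 | 14.3% and 8.6% | 0 to 3 of 30 | 0% to 10.0% |
| 0 | 5 | 0% and 14.3% | 5 of 35 | 14.3%, no range |

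The third row looks like an improvement and still allows three new findings. The last row hides nothing. Anterior chamber cells and flare should be close to that case, since a Tyndall score above 0 is excluded at entry (Protocol 4.2, criterion 5). With a larger n and the same counts, the bounds on the number of eyes do not change and the upper percentage, v/(n − b), becomes smaller.

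**Step 2: the Week 32 denominator.** Suppose 5 of 35 eyes are abnormal at baseline, 2 of those 5 leave at Week 8, and no eye changes. The table moves from 5/35 = 14.3% to (5 − 2)/(35 − 2) = 3/33 = 9.1%, although no eye improved. This concerns Week 32. Patients discontinued at Week 8 still have their Visit 6 examination.

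**Step 3: precision.** A paired count would be imprecise. 3 of 30 is 10.0% (exact 95% confidence interval 2.1% to 26.5%), and 0 of 30 has an upper limit of 11.6%.

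**Step 4: which paired summary.** A count of worsened eyes alone picks up grading noise in one direction. With an assumed 5% error at the visit examination, 30 eyes at risk give 30 × 0.05 = 1.5 false new findings per parameter and visit. The 5 eyes abnormal at baseline give 5 × 0.05 = 0.25 false resolutions. A two-way table shows both, and read as rates they agree (5% each way). Taking the worst of three examinations makes the problem larger: 1 − (1 − e)³ is 5.9%, 14.3% and 27.1% for e = 2%, 5% and 10%, if errors are independent.

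**The case against.** The strongest objection is that this is a choice of display and breaks no rule. Adverse events are the only safety endpoint (Protocol 7.1.3), and Protocol 9.3.3 plans only adverse event summaries, so SAP 6.3 and 6.4 already go further. Adverse event recording is broad. Protocol 8.1 and 8.3 cover any unfavorable and unintended sign, and Protocol 8.2 requires clinically relevant changes in examined parameters to be reported. These events are tabulated by severity, relationship and study period (SAP 6.1). Every examination is listed (Listings 16.2.8.2 and 16.2.8.3), and with about 35 patients new findings could be counted by hand.

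Most of this stands, and it is why the point is minor. What remains is that Protocol 8.2 applies a relevance filter, that the adverse event tables count subjects rather than eyes, and that a listing is not a count.

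A reader might infer three stronger points that the documents do not support:

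- **A safety signal would be concealed.** Clinically relevant changes should reach the adverse event tables, and the individual examination data are listed.
- **SAP 2.5 promises a worst-case safety table that is missing.** Its worst-case wording is conditional, and may already be served by the efficacy analysis in SAP 5.1 (Table 14.2.1.1.4).
- **The SAP treats intraocular pressure and the examinations inconsistently.** SAP 2.9 assigns change from baseline to continuous data and frequencies to categorical data, and both are handled accordingly.

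**Conclusion.** The point holds as a minor, cheap improvement. The planned tables show net change only, cannot give the number of eyes newly abnormal or worsened, and at Week 32 do not compare the same eyes. The consequence is mainly confined to findings not judged clinically relevant or not reported as adverse events. No efficacy result and no count of treatment-emergent events changes.

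The non-identification in Step 1 is arithmetic and needs no assumption. Its practical size rests entirely on assumed counts and on n = 35. The full mock shells are a separate document (SAP 1) and were not available. They could already contain a shift layout, but neither the SAP text nor its table list calls for one.

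**What to change.** Keep the by-visit frequencies in SAP 6.3 and 6.4, and add to both sections and to Tables 14.3.4 and 14.3.5:

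> For each parameter, a shift table from baseline to Weeks 4, 8 and 32 will be given on the scale recorded in the eCRF (for example normal / abnormal, not clinically significant / abnormal, clinically significant), separately for study eyes and treated non-study eyes, among eyes with both a baseline and a visit result. Worsening and improvement will both be shown as n/N. For other abnormal findings, newly present and resolved findings will be shown.

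Two notes belong with it. Cornea Epithelial Changes will say little about new abnormality, because every study eye enters with Grade 3 central staining (Protocol 4.1, criterion 3). A worst post-baseline column is best left out; if included, it needs a footnote that it is biased upward without a control arm.

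The pairing removes the artifact of a changing set of eyes but does not recover Week 32 data for patients who left.

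**Cost.** The change is to SAP and shell wording and uses data already collected at Visits 2, 4, 6 and 7. If each of the 20 slit lamp and 3 external parameters is one categorical result, the addition is 23 × 2 eye groups × 3 visits = 138 small shift panels. Seven of the 20 slit lamp parameters are other abnormal findings and reduce to present or absent. The recorded scale should be confirmed first: SAP 1.3.4.3 describes three categories for eight structures, not for the 20 parameters, and Protocol 6.1.1 leaves grading to the Manual of Procedures. The downside is more safety output. If the shells already show shifts, one SAP sentence is enough.
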